6.4.2. Analysis Methods

Vital signs records with partial dates (any of day/month/year is missing) will not be used in the analysis but will be listed.

Descriptive statistics of continuous vital sign parameters and body temperature will be calculated for observed values and changes from baseline at each scheduled time point.

Shift tables will be provided summarizing the shift in vital sign and body temperature values from baseline over time with respect to abnormality criteria (low, normal, high) for each parameter by study phase.

A cross-tabulation of the worst abnormalities versus baseline per parameter and study phase will be presented including also the number of participants per abnormality, the number of participants with treatment emergent abnormalities per abnormality.

- A tabulation of percentage and number of the participants who have treatment-emergent worst abnormalities per parameter and study phase will be included.
- A listing including all parameters for participants with at least one treatment-emergent abnormality (on actual values or change from baseline) is provided. Additional vital signs assessments corresponding to the rash eCRF pages will be only listed as applicable.

6.5. Physical Examination

The physical examination findings and abnormalities will be listed.

7. VIRAL GENOME SEQUENCE ANALYSIS

Viral genome sequence analysis will be performed to identify pre-existing baseline polymorphisms and to evaluate emergence of genetic variations (including substitutions) associated with JNJ-56136379, JNJ-3989, and/or ETV or TDF treatment on both nucleotide and/or amino acid level.

Sequencing of the HBV genome will be performed to monitor HBV variants present at the time points indicated in Section 7.1.

Virology results will be presented by specified timepoints and genetic region and position of interest. A separate virology report will be prepared.

7.1. Time Points and Samples

When analyzing sequencing data, the focus will be on genetic variants at

- Time Point of Sequence at Baseline (BLSEQ): Last available pre-first dose time point in the study with sequence data available
- Time Point of Sequence at End of Study Agent (last available on-treatment time point, with a specific focus on subjects not meeting the NA treatment completion criteria)
- Time Point of Sequence at Virologic Breakthrough: time point with sequence data available closest to the time point of virologic breakthrough (FTPT) (see Section 5.4.15.1 for virologic breakthrough definition)
- Time Point of Sequence at Virologic Flare: time point with sequence data available closest to the time point of Virologic flare (see Section 5.4.14.1 for virologic flare definition)

- Time Point of Sequence at End of Study (ESSEQ): last available off-treatment post-baseline time point in the study with sequence data available
- Time Point of Sequence at Re-treatment during Post-treatment Follow-up: time point with sequence data available closest to time point where re-treatment criteria is met (see Section 5.4.4)
- Aggregated Post-Baseline Study Period (ASSEQ): entire post-baseline study period, aggregate of all available time points in the study with sequence data available
- Aggregated Post-Baseline Treatment Period (ATSEQ): entire post-baseline treatment period, aggregate of all available post-baseline time points during the treatment phase with sequence data available

The sequencing of samples after baseline may be triggered by the sponsor virologist based on changes in HBV DNA levels observed in each individual subject and the limits of the sequencing assay.

7.2. Definitions

(Baseline) Genetic variations (i.e. aka baseline polymorphisms) are defined as changes (on the amino acid or nucleotide level) in the subject viral sequence compared to a HBV genotype specific reference viral sequence and/or the universal HBV reference sequence (NCBI ID X02763). The reference sequence to be used is provided in the database. The reference viral sequences to be used are:

Virus	Genotype	NCBI genbank accession	NGS isolate name	Sanger genbank accession	Sanger isolate name
HBV	A	X02763	adw2	X02763	adw2
HBV	B	AB219428	PNN3	D00329	pJDW233
HBV	C	GQ924620	M38	AB014362	03D03HCC
HBV	D	AF121240	11066	V01460	ayw
HBV	E	AB106564	GA325	X75657	ayw4
HBV	F	AY090458	70H	X75658	adw4q
HBV	G	AF160501	IG29227	AB064311	USG825
HBV	H	FJ356716	CL150171	AY090460	LAS2523
HBV	I	EU833891	H4536-07		

Wild type: If at certain position the amino acid/nucleotide in the subject sequence matches the reference sequence, that is no genetic variation is present at that position, the virus is considered to be wild type at that position.

Emerging viral variation: If at certain position a genetic variation is absent at baseline but present at later time point, the genetic variation is considered to be emerging at that time point. For NGS, emerging will be defined based on the frequency of variant at baseline and at the later time point. “Absent at baseline” is defined as a frequency of variant below 1% (<1%). “Present at later point” is defined as a frequency of variant equal or greater than 15% ($\geq 15\%$) at the later time point.

Enriched genetic variations: are exclusively defined for NGS analysis. If at a certain position a genetic variation has a frequency of variant of $\geq 1\%$ but $< 15\%$ at baseline and a frequency of variant of $\geq 15\%$ at a later time point and an increase in read frequency of $\geq 15\%$.

7.3. Parameters to Analyze

At specified time points and for each list specified in the section below, the following parameters will be analyzed:

- Number (%) of subjects with a substitution at a specific position.
- Number (%) of subjects with a specific substitution.
- Number (%) of subjects with a specific substitution profile
- Number (%) of subjects with substitutions on amino acid level (overall and by HBV genotype (A, B, C, D, E, F, G, H, I, J and Other))
 - in the HBV core protein,
 - at HBV core protein positions of interest,
 - at positions of interest in the RT-domain of the polymerase,
 - at positions of interest in the major hydrophilic loop of HBsAg.
- Number (%) of subjects with substitutions on nucleotide level
 - at the binding site positions of JNJ-3989 (i.e. JNJ-3976 and JNJ-3924) (overall and by HBV genotype (A, B, C, D, E, F, G, H, I, J and Other)).
 - in the precore (genome position 1896) and basal core promotor (genome positions 1762/1764) region (overall, by HBV genotype (A, B, C, D, E, F, G, H, I, J and Other) and by baseline HBeAg status)
- Number (%) of subjects with treatment-emergent and enriched substitutions on amino acid level at post-baseline time points (as defined in Section 7.1) by substitution profile
 - at HBV core protein position of interest (list of 28 and 15 POI),
 - at positions of interest in the polymerase region,
 - at positions of interest in the major hydrophilic loop of HBsAg.
- Number (%) of subjects with treatment-emergent and treatment-enriched substitutions on nucleotide level at post-baseline time points (as defined in Section 7.1) by substitution profile
 - at the binding site positions of JNJ-3989 (overall and by HBV genotype (A, B, C, D, E, F, G, H, I and J)).

The focus will be on substitutions at a time point, emerging and enriched variations and reversion to wild type or baseline state. The above summaries will be repeated for genetic variations (not needed for CSR).

In the sequence analysis, sequences will be mapped to the respective genotype specific reference sequences after which nt changes and aa substitutions will be annotated compared to the respective genotype specific reference (see Table in Section 7.2). In addition, the X02763 (HBV genotype

A), which is the master reference sequence of the HBV db, will be used as universal reference sequence.

All NGS data will be collected using a nt and aa read frequency cut-off of ≥ 0.01 . For the analysis of baseline nt changes and/or aa substitutions in terms of frequency of variant and impact on treatment outcome, a read frequency cut-off of ≥ 0.15 will be used. The analysis of treatment-emergent nt changes or aa substitutions will consider nt changes or aa substitutions absent at baseline (<0.01 read frequency) but present at a read frequency of ≥ 0.15 at later time points. Virology analyses based on NGS data will also evaluate treatment-enriched nt changes and aa substitutions, defined as present at baseline with a read frequency ≥ 0.01 but <0.15 and with an increase in read frequency of at least 0.15 post-baseline. A minimum increase in read frequency of 0.15 compared to baseline excludes small, potentially technical variations in the read frequency of minority nt changes and aa substitutions which are not expected to have clinical relevance. In addition, for subjects with treatment failure nt changes and aa substitutions detected with a read frequency ≥ 0.01 at baseline, at time of failure and at end of study will be described in a listing. The persistence of treatment-emergent nt changes and aa substitutions will be evaluated using a cut-off of ≥ 0.15 and ≥ 0.01 .

The applicability of the sequencing approach described here (eg, the 0.01 sensitivity limit) will be assessed during the development program and might be adapted if needed.

7.4. Positions & Genetic Variations of Interest

On the nucleotide level:

In the basal core promotor region:

- 1762 and 1764 (ECoRI numbering will be used)

In the precore region:

- 1896 (ECoRI numbering will be used)

In the basal core/precure region

- Combination of basal core promotor and/or precore region

In the JNJ-3989 binding pocket positions:

- JNJ-3976 (S Trigger)
 - Long list (N=21): 259, 260, 261, 262, 263, 264, 265, 266, 267, 268, 269, 270, 271, 272, 273, 274, 275, 276, 277, 278, and 279
 - Short list (N=17): 262, 263, 264, 265, 266, 267, 268, 269, 270, 271, 272, 273, 274, 275, 276, 277, and 278
- JNJ-3924 (X Trigger)

- Long list (N=21): 1779, 1780, 1781, 1782, 1783, 1784, 1785, 1786, 1787, 1788, 1789, 1790, 1791, 1792, 1793, 1794, 1795, 1796, 1797, 1798, and 1799
- Short list (N=17): 1782, 1783, 1784, 1785, 1786, 1787, 1788, 1789, 1790, 1791, 1792, 1793, 1794, 1795, 1796, 1797, and 1798
- In the JNJ-3976/JNJ-3924
- Combination of JNJ-3989 binding site positions JNJ-3976 and/or JNJ-3924

Amino acid level:

In the HBV core protein (based on putative binding pocket [[Bourne C. et al., 2006 & Katen S.P. et al., 2013](#)])

- Long list (n=47): 18, 19, 23, 24, 25, 26, 27, 28, 29, 30, 31, 32, 33, 37, 38, 102, 103, 105, 106, 107, 109, 110, 111, 114, 115, 116, 117, 118, 119, 122, 123, 124, 125, 126, 127, 128, 129, 131, 132, 133, 134, 136, 137, 138, 139, 140, 141
- Due to an insertion of 12 amino acids in the N-terminal part of core, the 47 HBV Core Protein positions of interest for HBV genotype G are 30, 31, 35, 36, 37, 38, 39, 40, 41, 42, 43, 44, 45, 49, 50, 114, 115, 117, 118, 119, 121, 122, 123, 126, 127, 128, 129, 130, 131, 134, 135, 136, 137, 138, 139, 140, 141, 143, 144, 145, 146, 148, 149, 150, 151, 152, 153.

Based on some recent more detailed published structural data ([Klumpp K. et al., 2015](#), [Qiu Z. et al., 2016](#), [Zhou Z. et al., 2017](#), & [Tu J. et al., 2017](#)), and some in house structural analysis, a more shortened list of core positions of interest can be defined:

- Short list (n=28): 23, 24, 25, 29, 30, 33, 37, 38, 102, 105, 106, 109, 110, 118, 122, 124, 125, 127, 128, 129, 132, 133, 134, 137, 138, 139, 140, 141
 - Due to an insertion of 12 amino acids in the N-terminal part of core, the 28 HBV Core Protein positions of interest for HBV genotype G are 35, 36, 37, 41, 42, 45, 49, 50, 114, 117, 118, 121, 122, 130, 134, 136, 137, 139, 140, 141, 144, 145, 146, 149, 150, 151, 152, 153
- Short list (n=15): 23, 24, 25, 29, 30, 33, 37, 105, 106, 109, 110, 118, 124, 127, 128.
 - Due to an insertion of 12 amino acids in the N-terminal part of core, the 15 HBV Core Protein positions of interest for HBV genotype G are 35, 36, 37, 41, 42, 45, 49, 117, 118, 121, 122, 130, 136, 139, 140

In the pol/RT protein:

- 169, 173, 180, 181, 184, 194, 202, 204, 236, 250

See below breakdown of relative amino acid position of the 10 POI in the RT-domain of polymerase by HBV genotype.

HBV GT-A		HBV-GT-B/C/F/H/I		HBV GT-D		HBV-GT-E/G	
POL number	RT number	POL number	RT number	POL number	RT number	POL number	RT number
517	169	515	169	504	169	514	169

HBV GT-A		HBV-GT-B/C/F/H/I		HBV GT-D		HBV-GT-E/G	
POL number	RT number	POL number	RT number	POL number	RT number	POL number	RT number
521	173	519	173	508	173	518	173
528	180	526	180	515	180	525	180
529	181	527	181	516	181	526	181
532	184	530	184	519	184	529	184
542	194	540	194	529	194	539	194
550	202	548	202	537	202	547	202
552	204	550	204	539	204	549	204
584	236	582	236	571	236	581	236
598	250	596	250	585	250	595	250

In the major hydrophilic loop of the S-protein region (linked to vaccine escape):

- Amino acids 99 to 169
- Positions of interest: 116, 118, 120, 126, 129, 130, 131, 133, 134, 141, 142, 143, 144, 145, 164, 195, and 196.

7.5. Analysis Methods

Frequencies and percentages will be presented at the time points specified above for the specified parameters. The denominator is the number of subjects with sequencing data at the selected time point. For comparison of amino acid or nucleotide levels to universal HBV reference sequences descriptive summaries will be performed by subgroups (HBeAG status at screening and HBV genotypes) intervention arm. For comparison of amino acid or nucleotide levels to HBV genotype-specific reference sequences, descriptive summaries will only be performed by subgroup HBV genotypes and intervention arm.

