 Urinalysis by dipstick: specific gravity, pH, glucose, protein, blood, ketones, bilirubin, urobilinogen, nitrite, leukocyte esterase, and microscopic analysis if needed.
 In case of a positive dipstick result, a urine sample will be set aside for additional examination of the positive parameter at the central laboratory (eg, quantification as applicable).
- y. Urine sample for selected renal biomarkers including retinol binding protein and beta-2-microglobulin.
- z. Only applicable to participants who are enrolled at a site with an on-site Fibroscan device. A Fibroscan assessment will only be done at baseline if it was not done at screening.
- aa. HBcrAg and HBV RNA samples may be batched and only selected samples may be tested at the sponsor's discretion. Samples can be used for assessment of other serologic/virologic markers of HBV.
- bb. Sequencing at baseline (Day 1 predose) will be performed by default if HBV DNA levels are within the ranges required for the sequencing assay; other samples may be sequenced based on the sponsor virologist's request.
- cc. Participants with undocumented (ie, no lab report) HBeAg status as part of their medical history must first complete HBeAg testing and have results reviewed by the investigator to confirm if they qualify for study participation. Documented HBeAg status within 12 months prior to screening is acceptable.
- dd. Quantitative HBeAg assessment will only be performed in participants who are defined HBeAg-positive at screening based on a qualitative HBeAg assay.

- ee. Exploratory serology samples may be analyzed at the sponsor's discretion. Samples may be used to assess virologic or serologic markers of HBV.
- ff. All participants will have sparse PK sampling. For all samples, the time of the preceding 2 intakes of oral study intervention (JNJ-6379/placebo and NA) and the time of PK sampling should be recorded. Sparse PK sampling is not required if the participant is part of the intensive PK subgroup and has an intensive PK sampling at the same visit.
- gg. One sample at any time between 2 and 8 hours after JNJ-3989/placebo dosing. Before leaving the study site, the participant's wellbeing should be confirmed.
- hh. Only in case of early withdrawal.

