5.1. Inclusion Criteria

Each potential participant must satisfy all of the following criteria to be enrolled in the study:

- 1. Adult male or female participants 18 (or the legal age of consent in the jurisdiction in which the study is taking place) to 65 years of age, inclusive.
- 2. Participants must be medically stable, with the exception of HBV disease, on the basis of physical examination, medical history, vital signs, and 12-lead ECG performed at screening. If there are abnormalities, they must be consistent with the underlying illness in the study population. This determination must be recorded in the participant's source documents and initialed by the investigator.
- 3. Participants must have chronic HBV infection documented by serum HBsAg positivity at screening. In addition, chronicity must be documented by serum HBsAg positivity at least 6 months prior to screening or alternative markers of chronicity (HBeAg positivity or HBV DNA positivity at least 6 months prior to screening, ALT elevation above ULN at least 6 months prior to screening without another cause than HBV infection, liver

biopsy, or documented transmission event at least 6 months prior to screening).

Note: if documentation of chronicity (as mentioned above) at least 6 months prior to screening is not available, participants may be included if HBsAg positive and negative for immunoglobulin M (IgM) antibodies to HBc antigen at screening.

- 4. Participants who are **not currently treated** (defined as not having been on HBV treatment, including NAs and IFN products within 6 months prior to screening), including **treatment-naïve** participants (defined as never having received HBV treatment, including NAs and IFN products) should have:
 - a. Serum HBV DNA at screening ≥2,000 IU/mL for HBeAg-negative participants and ≥20,000 IU/mL for HBeAg-positive participants, AND
 - b. ALT levels at screening <10x ULN AND >ULN on two measurements at least 3 months apart (one of which is at screening).
- 5. Virologically suppressed participants should:
 - a. be on stable HBV treatment, defined as currently receiving NA treatment (ETV, TDF, or TAF) for at least 6 months prior to screening and having been on the same NA treatment regimen (at the same dose) as used in this study (see Section 6.1) for at least 3 months at the time of screening, AND
 - b. have serum HBV DNA <60 IU/mL on two measurements at least 6 months apart (one of which is at screening), AND

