7.5.2. Post-Baseline

- Time of Virologic Breakthrough (if applicable)

For subjects with virologic breakthrough, the incidence of treatment-emergent (NGS) and treatment enriched genetic variations (with primary focus on substitutions) will be tabulated in

frequency outputs (n, %) and the genetic variations will be listed for all subjects with paired baseline and post-baseline sequencing data.

The return to baseline for subjects with virologic breakthrough and treatment-emergent genetic variations at time of virologic breakthrough will be tabulated in frequency outputs based on NGS data, as well as the treatment-emergent genetic variations in subjects who did not return to baseline.

- Time of End of Treatment

For subjects who don't meet the NA treatment completion criteria, the incidence of treatment-emergent and treatment-enriched variants (with primary focus on substitutions) will be tabulated in frequency outputs (n, %) and the genetic variations will be listed for all subjects with paired baseline and post-baseline sequencing data.

The return to baseline for subjects who don't meet the NA treatment completion criteria and treatment-emergent genetic variations end of treatment will be tabulated in frequency outputs based on NGS data, as well as the treatment-emergent genetic variations in subjects who did not return to baseline.

- Time of Virologic /Clinical Flare (if applicable)

For subjects with virologic/clinical flare, the incidence of treatment-emergent (NGS) and treatment-enriched genetic variations (with primary focus on substitutions) will be tabulated in frequency outputs (n, %) and the genetic variations will be listed for all subjects with paired baseline and post-baseline sequencing data.

The return to baseline for subjects with virologic/clinical flare and treatment-emergent genetic variations at time of virologic/clinical flare will be tabulated in frequency outputs based on NGS data, as well as the treatment-emergent genetic variations in subjects who did not return to baseline.

- Time of Re-treatment during Post-treatment Follow-up

For subjects who meet re-treatment criteria during follow-up, the incidence of treatment-emergent and treatment-enriched variants (with primary focus on substitutions) will be tabulated in frequency outputs (n, %) and the genetic variations will be listed for all subjects with paired baseline and post-baseline sequencing data.

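### The SAP's single denominator for sequencing percentages does not fit treatment-emergent and enriched variants, which cannot be classified without a baseline sequence

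*SAP*

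**What the plan says.** SAP 7.5 sets a general rule for the sequencing frequencies and percentages: "The denominator is the number of subjects with sequencing data at the selected time point". It names no other denominator.

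SAP 7.2 defines emergence as a comparison with baseline: if at some position "a genetic variation is absent at baseline but present at later time point", the variant is emerging. For next-generation sequencing, absent means a read frequency below 1% and present means at least 15%. Enriched means 1% to below 15% at baseline, then at least 15% with a rise of at least 15 percentage points.

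SAP 7.3 asks for "Number (%) of subjects with treatment-emergent and enriched substitutions on amino acid level at post-baseline time points" and refers to SAP 7.1 for those time points. They include breakthrough, flare, re-treatment, end of study, and two aggregates over the whole post-baseline study and treatment periods. A parallel item covers nucleotide changes at the JNJ-3989 binding sites.

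SAP 7.5.2 has a paragraph each for breakthrough, end of treatment, flare and re-treatment. Each says that emergent and enriched variants will be tabulated as n and %, and that the "genetic variations will be listed for all subjects with paired baseline and post-baseline sequencing data".

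On whether a baseline sequence will exist, Protocol 1.3.1, footnote bb, says: "Sequencing at baseline (Day 1 predose) will be performed by default if HBV DNA levels are within the ranges required for the sequencing assay". Under Protocol 5.1, criterion 5, virologically suppressed participants must "have serum HBV DNA <60 IU/mL on two measurements at least 6 months apart", one of the two measurements being at screening.

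**The concern.** The 7.5 denominator suits a prevalence table, where anyone sequenced at the visit can be compared with the reference sequence. It does not suit a table of change from baseline. A participant sequenced at a rebound visit with no usable baseline sequence enters the denominator but cannot enter the numerator, so the printed percentage falls for a reason unrelated to resistance.

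This situation is foreseeable. Participants who enter suppressed may have too little HBV DNA to sequence at screening or Day 1. Later they may stop NA and rebound. A virologic flare in SAP 5.4.14.1 requires off-treatment HBV DNA above 200 IU/mL, and the HBV DNA thresholds for re-treatment in Protocol 6.7 start above 2,000 IU/mL. At that point sequencing may become possible. The sequenced set is also selected after randomization, so the dilution could differ between arms.

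At stake is the planned numerical summary of emergent resistance to JNJ-3989 and JNJ-6379. Protocol 2.3.2.2 lists viral resistance as a potential risk for both agents.

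**Working it through.** The documents give no sequencing yield, paired-sample count or emergent-variant rate, so there is no figure to reproduce. The check has two parts.

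**1. Which outputs have paired wording**

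| Output | Paired wording |
|---|---|
| Emergent/enriched n (%) at breakthrough, end of treatment, flare, re-treatment (SAP 7.5.2) | In the same sentence, attached to the listing; could be read to cover the table as well |
| Emergent/enriched n (%) at end of study (SAP 7.1, 7.3) | None |
| Emergent/enriched n (%) over the aggregated periods (SAP 7.1, 7.3) | None |
| Variant frequency at other post-baseline visits (SAP 7.5.2) | None; not needed for prevalence against the reference |

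So on the reading kindest to the SAP, the general rule in 7.5 still governs the end-of-study and aggregated outputs.

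**2. Size if the rule is applied literally**

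Let u be the share of participants sequenced at the time point who have no baseline sequence. Then

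reported % = (emergent / paired) × (1 - u).

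| u (assumed) | Reported/true | A 20% rate among paired participants prints as |
|---|---|---|
| 0 | 1.0 | 20% |
| 0.1 | 0.9 | 18% |
| 0.3 | 0.7 | 14% |
| 0.6 | 0.4 | 8% |

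To see what values of u are plausible, take the enrolment aim of 40% not currently treated (Protocol 4.1), which leaves 1 - 0.40 = 60% suppressed, or 270 of 450. Let s be the chance that a suppressed participant is sequenced at the time point relative to one not currently treated. Let b be the share of suppressed participants with a baseline sequence. Assume that every participant not currently treated has a baseline sequence. Then

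u = 0.6 × s × (1 - b) / (0.4 + 0.6 × s).

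| s | u if b = 0 | u if b = 0.5 |
|---|---|---|
| 0.05 | 0.07 | 0.035 |
| 0.10 | 0.13 | 0.065 |
| 0.25 | 0.27 | 0.14 |
| 0.50 | 0.43 | 0.21 |
| 1.00 | 0.60 | 0.30 |

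For example, with s = 0.25 and b = 0: 0.6 × 0.25 / (0.4 + 0.15) = 0.15 / 0.55 = 0.27. Across this grid, reported/true runs from about 0.97 (1 - 0.035) to 0.40 (1 - 0.60). Both s and b are assumptions.

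**The case against.** The strongest reply is that the authors saw the problem. The restriction to paired sequences appears in the four paragraphs of SAP 7.5.2 that deal with emergent variants, while the baseline and other-visit paragraphs simply list all subjects. A programmer could reasonably apply it to the tables too. That stands as far as it goes: for those four time points the SAP is ambiguous rather than shown to be wrong. It does not reach the end-of-study and aggregated outputs.

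It is also fair that low HBV DNA works both ways. SAP 7.1 says later sequencing may be triggered by HBV DNA changes and is subject to assay limits, so suppressed participants mostly stay out of the post-baseline denominator until they rebound. A reader might infer from the enrolment aim that 60% of the denominator is affected and that rates are understated 2.5-fold (1/0.4). The documents do not support this. The 60% is a share of planned enrolment, and u reaches 0.6 only if suppressed participants are sequenced as often as the others and none has a baseline sequence.

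Three further readings are tempting and should be set aside:

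- **Missing baseline counted as absent.** This would make every polymorphism look emergent, but SAP 7.2 defines absent as a frequency below 1%. A missing sequence has no frequency.
- **Return-to-baseline tables share the fault.** They are already limited to participants with emergent variants, who must have a baseline sequence. Widening that denominator to all paired participants would itself dilute the result.
- **The 15% baseline ceiling in the enriched definition is an error.** A variant rising from 15% to 100% does fall outside both labels, and the stated reason in SAP 7.3, "A minimum increase in read frequency of 0.15 compared to baseline excludes small, potentially technical variations in the read frequency", supports the minimum rise rather than the ceiling. But SAP 7.3 uses the same 15% cut-off to identify baseline variants, and later frequencies are still tabulated and listed. The ceiling is a debatable choice.

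Finally, emergence of mutations is an exploratory endpoint, summarised descriptively with subject-level listings. No error rate, power figure, or primary or key secondary result depends on it.

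**Conclusion.** The concern holds in a limited form. The denominator written in SAP 7.5 does not match the definitions in SAP 7.2 for treatment-emergent and enriched variants. SAP 7.5.2 may repair this for four time points, but nothing repairs it for end of study and the aggregated periods. Applied literally, the rule understates those rates by the factor (1 - u). The documents do not give u. Over an assumed range of 0 to 0.6 the reported rate is 1.0 to 0.4 times the rate among classifiable participants, the lower end being an extreme case. Suppressed participants who rebound off treatment are the expected main source; this is an inference from the entry criterion and the condition on baseline sequencing, not something the documents show. It cannot be said from the documents that emergent resistance will be misstated, only that the written rule permits it and leaves the size uncontrolled.

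**What to change.** In SAP 7.5, keep the present denominator for prevalence tables and add that percentages for treatment-emergent and treatment-enriched variants use participants with both a baseline and a post-baseline sequence. Apply this at every post-baseline time point and aggregated period in SAP 7.1. Report, by arm and treatment history, how many participants were sequenced without a baseline sequence, and describe their variants against the reference sequence only. Leave the return-to-baseline denominator and the enriched definition as they are.

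The cost is SAP wording and table programming, with no new sequencing. The downside is smaller denominators, so the percentages will be less precise.
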